3.2.3 Time To Progression (TTP)

- The Time to Progression (TTP) will be calculated as the number of days from the date of first administration of BGB324 to the date of radiological progression of disease first observed, according to the overall response evaluation (progressive disease, measurement proven or progressive disease, symptomatic deterioration). If a subject died without any radiological assessment, the progressive disease date is date of death;

Patients who do not have progressive disease at the end of study or withdrawal will have their TTP censored. In these patients, the censoring date is defined as the last date on which progression status was assessed. Censoring general rules for TTP are provided within [Table 1](#) below.

Table 1: Censoring Rules for TTP

Reason for censoring	Rule
No baseline evaluable or post-baseline radiological assessment	Date of first treatment administration
Two or more not evaluable (NE) protocol specified assessments, i.e. scheduled assessments, before progressive disease	Date of last evaluable disease protocol specified assessment before the second protocol specified NE assessment
No progressive disease	Date of last evaluable radiological assessment
Treatment discontinuation for undocumented progression	Date of last evaluable radiological assessment
Treatment discontinuation for toxicity or other reason	Date of last evaluable radiological assessment

* An assessment is considered NE when no imaging/measurement is done at all at a particular time point, or only a subset of lesion measurements are made at the time point. The participant is considered NE at that time point.

3.3 Pharmacokinetic End-points

Pharmacokinetic analysis will be managed by Bergen Bio then will not be part of this SAP.

3.4 Pharmacodynamic End-points

Pharmacodynamic analysis will be managed by Bergen Bio then will not be part of this SAP.

4 Study Design

4.1 Discussion of Study Design

This is a multi-center open-label Phase 1/2 study of BGB324 as a single agent (Run-in Cohort) and in combination with erlotinib (Arms A, B and C) in patients with Stage IIIb or Stage IV NSCLC.

At time of amendment 5, patient recruitment into the Run-In cohort (BGB324 monotherapy) and Arm A (BGB324 dose escalation in combination with erlotinib) has completed and the RP2D has been confirmed. Patients that remain on treatment in the Run-In cohort or Arm A must be followed up in accordance with the protocol schedule.

This study is anticipated to be conducted at approximately 10 sites in the US and in Europe (the number of sites and the involvement of European sites may be revised to reflect changes in recruitment rates), and will enroll up to approximately 60 patients with histologically- or cytologically-confirmed Stage IIIb or Stage IV NSCLC.

It is anticipated that up to six patients will be enrolled in the Run-in Cohort, 18 patients in Arm A, up to 25 patients in Arm B, and up to 14 patients in Arm C. Recruitment into Arm C may be stopped if Arm B completes recruitment or is stopped before the 14 patient target is reached. Patients already enrolled into Arm C at that time will be allowed to continue in the study in accordance with the protocol.

Prior to starting dosing of BGB324 in combination with erlotinib, the safety and tolerability of single agent BGB324 will be assessed in the Run-in Cohort (Phase 1) in patients who have either exhausted existing licensed therapies or are unsuitable for existing licensed therapies

for NSCLC. A minimum of 6 patients must each receive at least 1 continuous 21-day cycle of BGB324 before enrolment into Arm A can commence.

Arm A (Phase 1) incorporates a standard 3+3 design to determine the dose of BGB324 that can be safely administered in combination with erlotinib in patients who have received prior treatment with erlotinib. To confirm the RP2D for Arms B and C, loading dose schedules, loading doses and daily dose levels will be explored in Arm A. Dosing schedules will be revised in response to reported toxicities, DLT experience and SMC recommendations (Table 4 of the protocol).

When the RP2D dose of BGB324 is identified and the dose of erlotinib to be administered in combination with BGB324 is confirmed, the Phase 2 part of the study will start and Arms B and C will open simultaneously to enrolment.

Arm B will incorporate a two-stage design to evaluate the safety and tolerability, pharmacokinetics, pharmacodynamics and clinical activity of BGB324 in combination with erlotinib in patients with an activating EGFR mutation (including exon 19 deletion or exon 21 [L858R] substitution or other rearrangement of the EGFR gene) who are T790M negative and who have progressed after receiving treatment with an approved EGFR inhibitor (i.e. erlotinib, afatinib or gefitinib). Patients who have previously been treated with a T790M inhibitor (i.e. osimertinib) and who subsequently progressed will not require T790M testing.

Arm C will evaluate the safety and tolerability, PD and clinical activity (time to progression) of BGB324 when administered in combination with erlotinib in patients with an activating EGFR mutation (including exon 19 deletion or exon 21 [L858R] substitution or rearrangement of the EGFR gene mutation) who have received ≥ 12 weeks treatment with erlotinib without disease progression.

In all parts of the study, BGB324 will be self-administered orally according to a daily schedule during continuous 21-day treatment cycles.

[figure not shown]
Erlotinib will be self-administered orally according to a daily schedule during continuous 21-day treatment cycles (Arms A, B and C only).

Both drugs will be taken with water in the morning. BGB324 should be administered in the hour following erlotinib administration and at least 2 hours before breakfast.

Patients will be allowed to continue BGB324 treatment (as a single agent or in combination with erlotinib) if, in the opinion of the Investigator, they continue to derive clinical benefit or until unacceptable toxicity, disease progression, death or withdrawal of consent. Patients who stop BGB324 treatment will be withdrawn from the study.

An outline of the study design is provided in Figure 1.

Phase I- BGB324 Monotherapy and BGB324 Dose Escalation

Phase II- BGB324 in Combination with Erlotinib

[figure not shown]

Figure 1: BGB004 study Design Outline

4.2 Study Treatment

BerGenBio ASA will provide BGB324 to each study site.

Erlotinib will be obtained and administered following institutional practices.

4.2.1 Treatment Schedule and Administration of BGB324

BGB324 will be self-administered orally on an empty stomach according to a daily schedule during continuous 21-day treatment cycles.

The BGB324 dose will be based on the cohort and study arm to which the patient is enrolled. BGB324 should be administered with water in the morning at least 2 hours before breakfast and best efforts should be made to administer BGB324 at the same time each day, other than study visit days when BGB324 should be administered during the visit.

Patients will record their dosing at home in a dosing diary that will be reviewed at each study visit by the site staff. Patients will be instructed as to the importance of following the dosing instructions they have been provided with and for maintaining an accurate and up-to-date dosing record. Patients will also be instructed to bring their dosing diary and all BGB324 bottles, including unused and empty bottles, with them to each study visit. The site staff will record the amount of used and unused BGB324 capsules at study visits.

4.2.2 Treatment Schedule and Administration of Erlotinib

Erlotinib will be self-administered orally with BGB324 on an empty stomach according to a daily schedule during continuous 21-day treatment cycles. Best efforts should be made to administer erlotinib in the morning at the same time each day, other than on the morning of study visit days when erlotinib should be administered during the visit. Erlotinib should be administered with water. Patients will be instructed to take their erlotinib dose first followed by BGB324 within the next hour.

Patients will record their dosing at home in a dosing diary that will be reviewed at each study visit by the site staff. Patients will be instructed as to the importance of following the dosing instructions they have been provided with and for maintaining an accurate and up-to-date dosing record. Patients will also be instructed to bring their dosing diary and all boxes of erlotinib, including unused and empty boxes, with them to each study visit. The site staff will record the amount of used and unused erlotinib at study visits.

The details for management of dose modification are specified in the protocol section 11.3.

4.3 Study Schedule

The study period will consist of screening, treatment and an end-of-study visit. The end-of-study visit will occur 28 days after the patient has discontinued BGB324 treatment.

A detailed Schedule of Events can be found in the study protocol, Section 10.

[Table 2](#) provide the study schedule.

4.3.1 Screening

Patient eligibility for the study will be determined within 28 days prior to the first dose of BGB324 (Cycle 1 Day 1). Screening assessments will be conducted according to the study protocol Section 10.1.1 and Table 5.

In Arm B, the screening period may be extended to accommodate T790M confirmation from tumor biopsy. Patients who have previously been treated with a T790M inhibitor (i.e., osimertinib) and who subsequently progressed will not require T790M testing. All other assessments including scans should be conducted in the 28-day screening period.

4.3.2 Treatment

Eligible patients will visit the study site to receive study drug and protocol-specified procedures according to Section 10.1.2 to Section 10.1.4 and Table 5 of the protocol. The treatment period will consist of continuous 21-day treatment cycles.

All patients will be carefully monitored throughout Day 1 to Day 4 in Cycle 1 and will attend the clinic on Cycle 1, Day 8, Cycle 1, Day 9 and Cycle 1, Day 15 (and Day -1 in Arms A).

Patients will attend the clinic once per week (on Cycle 2, Day 1, Cycle 2, Day 8 and Cycle 2 Day 15) during Cycle 2 and then once per cycle (on Day 1) thereafter up to 12 months of treatment (Cycle 17). Patients who remain on study after 12 months will attend the clinic every 2 Cycles (6 weekly).

Patients who do not receive loading doses as assigned but are considered suitable for daily dose treatment should attend the clinic for additional ECG assessments. Twice weekly triplicate ECGs should be conducted during Cycle 1, Day 8 – Day 15 and Cycle 1, Day 15 – Day 21.

Additional visits will be scheduled for disease assessment at the end of every two cycles (6 weeks) cycles. The frequency of scans may be extended to the end of every 3 cycles after 12 weeks (4 cycles) and every 4 cycles after 24 weeks (8 cycles). Patients who remain on study for 12 months or longer may have their scans extended to a frequency of 6 months unless disease progression is suspected in which case a scan should be conducted at an earlier time point.

Patients will continue to receive BGB324 (in combination with erlotinib or as a single agent) for as long as, in the opinion of the Investigator, they continue to derive clinical benefit or until disease progression, unacceptable toxicity, death or withdrawal of consent.

In the event of erlotinib-related toxicities in Arms A, B and C, patients may be allowed to continue receiving BGB324 as a single agent until disease progression unless unacceptable toxicity, death or withdrawal of consent). Patients who stop BGB234 treatment will be withdrawn from the study.

4.3.3 End of Study Visit

Patients will return to the study site for an end-of-study visit 28 days after the last dose of study drug (or at study withdrawal) according to Section 10.1.5 and table 5 of the protocol.

If BGB324-related toxicities continue beyond this follow-up period, patients will be followed until all BGB324-related toxicities have resolved to \leq Grade 1, stabilized or returned to baseline. If necessary, follow-up monitoring for AEs may be conducted over the telephone.

Table 2 Schedule of Events

Cycle		1												2							W ≥ 3			End-of- 28 days after last dose
Week		1(x)						2(x)			3(x)		4(x)		5(x)		6(x)			>7				
Cycle Day	28 to 0 Screening	-1 Arm A	1	2	3	4	5-7	8	9	10-14	15	16- 21	1	2-7	8	9-14	15	16-20	21	1	2- 20	21		
Visit window (+/-) days		0	0	0	0	0	0	0	0	0	0	0	+2	0	+	0	+1	0	+5	+2	0	+5	+7	
Clinic visit	X	X	X	X	X	X		X	X		X		X		X		X			X	X	X	X	
Informed consent	X																							
Demographics	X																							
Medical history	X																							
Cancer history and treatments	X																							
Inclusion/Exclusion	X																							
ECOG performance status	X												X								X		X	
Physical examination ^a	X ^a	X	X					X			X		X		X		X			X			X ^a	
Vital signs ^b	X	X	X	X	X	X		X	X		X		X		X		X			X			X	
12-Lead triplicate ^{c, v} ECG	X	X	X	X	X	X		X	X		X		X		X		X			X			X	
Pregnancy test ^d	X	X ^e	X																		X			X
Clinical chemistry ^f	X	X ^e	X	X	X	X		X			X		X		X		X			X			X	
Hematology ^g	X	X ^e	X	X	X	X		X			X		X		X		X			X			X	
Coagulation ^h	X	X ^e	X					X			X		X							X			X	
Urinalysis ⁱ	X	X ^e	X					X			X		X		X		X			X			X	
echocardiogram or MUGA scan ^t	X																			X			X	
PK blood sampling ^j		X	X	X	X	X		X	X		X		X		X		X			X			X	
Tissue collection for PDI, m,k,q	X																			X			X _r	
Blood collection for PD _{m, l, k}	X																			X			X _s	
EGFR T70M status (Arm B)	X _u																							

Disease assessment ^{p,n}	X																						X			X	X
-----------------------------------	---	--	--	--	--	--	--	--	--	--	--	--	--	--	--	--	--	--	--	--	--	--	---	--	--	---	---

Abbreviations:; ECOG=Eastern Co-operative Oncology Group; MUGA=multi-gated acquisition; PD=pharmacodynamics; PK=pharmacokinetics

- a. Physical examination conducted at the screening and end-of-study (EOS) visits. A symptom-directed examination will be conducted at other visits.
- b. Blood pressure, pulse, respiratory rate, temperature. In addition, at screening, weight and height to be recorded.
- c. Triplicate 12-lead ECG, at least 5 minutes apart, after resting for ≥ 10 minutes in supine position during screening and during each visit (pre-dose). Patients who restart BGB324 following interruption for QTc prolongation should also have ECGs performed according to this schedule.
- d. For women of child-bearing potential to be repeated every 3 months, or if possibility of pregnancy is identified. A serum test must be performed at screening and the EOS visits; interim tests may be performed on urine samples.
- e. Unless conducted as part of the screening procedures within 3 days prior to Day 1.
- f. Clinical chemistry laboratory parameters: potassium, calcium, uric acid, electrolytes, blood urea nitrogen, total protein, total bilirubin, alanine aminotransferase, aspartate aminotransferase, creatinine, creatine phosphokinase, alkaline phosphatase, albumin, phosphorus, glucose, magnesium (plus amylase and lipase during screening ONLY).
- g. Hematology laboratory parameters: full blood count including differential white cell count, hemoglobin, hematocrit and platelets.
- h. Coagulation parameters: prothrombin time and/or international normalized ratio, activated partial thromboplastin time.
- i. Dipstick measurement of blood, nitrite, glucose, ketones, leukocytes, protein and pH. (Microscopic analysis is not required unless clinically indicated).
- j. Blood sampling for the determination of BGB324 / erlotinib in plasma will be collected in accordance with Table 6.
- k. In consenting patients (Arms A, B and C), tissue specimens may be collected for analysis of pharmacodynamics endpoints of Axl inhibition. The baseline tissue specimen should be collected after enrollment within 28 days before the first dose of BGB324. The on-study tissue collection may be performed any time after 14 days of continuous exposure to BGB324 in Cycle 1 or in Cycle 2. The EOS tissue collection should be made at the time of disease progression and prior to the end-of-study visit (derived from the lesion exhibiting disease progression). Detailed procedures for the collection, processing, storage and shipment of the samples will be provided in the laboratory manual.
- l. Blood will be collected for analysis of pharmacodynamic endpoints of Axl inhibition. The baseline sample should be collected after enrollment within 28 days before the first dose of BGB324. The on-study sample collection may be performed any time after 14 days of continuous exposure to BGB324 in Cycle 1 or in Cycle 2. The EOSEOS sample should be taken at the time of disease progression and prior to the EOS-visit.
- m. If a tissue specimen is being collected, the PD blood sample should be collected at the same visit.
- n. Disease assessment via RECIST Version 1.1.
- o. BGB324 and erlotinib (not Run-in Cohort) will be administered on an empty stomach. Both drugs will be taken with water in the morning. BGB324 should be administered in the hour following erlotinib administration and at least 2 hours before breakfast (except on those days when the patient attends the clinic). Patients should record dosing in the dosing diary provided.
- p. Disease assessment will be performed at the end of every 2 cycles (6 weeks) beginning with Cycle 2 (Day 21); the assessment may be performed up to 5 days before Day 21 (Day 17-Day 21) but attempts should be made to conduct the assessment as close to Day 21 as possible. Disease assessment may be performed prior to initiation of the next cycle, but results must be available prior to initiation of treatment and must confirm continued eligibility for next cycle. The frequency of scans may be extended to the end of every three cycles after 12 weeks (4 cycles) and every 4 cycles after 24 weeks (8 cycles). Patients who remain on study for 12months may have their scan frequency reduced to 6 monthly.
- q. For consenting patients' only (Arms A, B and C); performed any time after documentation of disease progression and prior to EOS visit. The tissue specimen should be derived from a lesion exhibiting progression.
- r. If not performed within previous 28 days.
- s. To be performed at the time of disease progression and prior to the EOS visit.
- t. Cycle 4 Day 1 and then at 6 monthly intervals and at EOS.
- u. Patients in Arm B must have EGFR T790M status confirmed during screening – Patients who have progressed on osimertinib and have previously progressed on an approved EGFR inhibitor i.e. afatinib, gefitinib) will not require additional T790M testing. T790M testing may be confirmed by blood test or biopsy. Samples collected and analyzed according to local procedures. The screening window of 28 days may be extended to allow for confirmation of T790M status.

- v. Patients who do not receive their assigned loading doses and continue to receive daily dose BGB324 should attend the clinic for additional ECG assessments between C1 D8 and D15 and between C1 D15 and the end of Cycle 1.
- w. Patients who remain on study post C17 will have a reduced visit schedule and will return to clinic every 2 cycles (+/-7 days)
- x. Patients receiving BGB324 who require daily steroids at doses of 10mg to 40mg (prednisolone equivalent) should be monitored at weekly intervals until the steroid dose level is less than 10mg: Assessment should include physical exam, vital signs, hematology, chemistry.

4.4 Concomitant Medication

4.4.1 Prior and Concomitant Therapies

No additional treatment for NSCLC may be taken during the study period.

Previous adjuvant therapy is permitted provided it has been completed for ≥ 6 months.

Previous radiotherapy for cerebral metastases is permitted providing this is complete for ≥ 2 weeks before the first dose of study drug (BGB324 or Erlotinib whichever comes first) provided the patient is neurological stable and does not require corticosteroids.

4.4.2 Concomitant Medication and Procedures

All prescription, non-prescription, or over-the-counter medications, including herbal remedies, taken by the patient at entry and during the study must be clearly documented in the eCRF.

The patients must be instructed that no additional medication will be allowed without the prior consent of the Investigator. Any medication considered necessary for the patient's safety and well-being may be given at the discretion of the Investigator.

Hematopoietic growth factors may be administered for the treatment of AEs such as neutropenic infections but should not be used to maintain the dose intensity of BGB324 in the Run-in Cohort or Arm A.

Patients who have evidence of treatment benefit after ≥ 1 cycle (21 days) of treatment in Arms B or C may receive hematopoietic growth factors to maintain BGB324 dosing.

Concurrent treatment with any agent known to cause Torsade de Points is an exclusion criterion for the study. A comprehensive list of these prohibited medications is provided in Appendix 3 of the protocol.

Anti-diarrheal medications (e.g. loperamide) may be administered according to standard practice for the management of diarrhea. Patients must be provided with anti-diarrheal medications to take home, which may be used if required.

Patients being treated with antacid histamine receptor 2 inhibitors or proton pump inhibitors on study entry will be excluded. The Investigator may initiate rescue treatment with these medications during the study, providing they are taken in the evening.

Patients receiving BGB324 who require the support of prednisolone (or equivalent) at 10mg to 40mg daily should be monitored at weekly intervals whilst receiving treatment. If a patient requires prednisolone (or equivalent) at daily doses above 40mg then BGB324 should be interrupted until the steroid dose is equivalent or less than 40mg daily, at which time weekly monitoring will be undertaken until the steroid dose is equivalent or less than 10mg.

Steroid restrictions do not apply to topical/ inhaled/ eye or nasal drops. If required, additional advice on the concomitant use of steroids with BGB324 should be obtained from the BerGenBio Medical Monitor.

4.5 Study Analysis Populations

There will be 3 analysis populations defined for the study analyses:

4.5.1 Enrolled Population

The Enrolled Population will include all patients who have signed the ICF and enrolled into the study (Enrolment date being defined as the date of the first protocol-defined screening procedure).

4.5.2 Safety Population

The Safety Population will be defined as all enrolled patients who receive at least one dose of BGB324 or Erlotinib.

4.5.3 Efficacy Population

The Efficacy Population will include all patients who receive ≥ 1 cycle of BGB324 and undergo an assessment of response post-baseline.

Patients who on review do not meet the protocol inclusion/exclusion criteria or have a major protocol deviation may be excluded from the efficacy analysis. This will be reviewed (and documented) on a per patient basis at the pre-database lock meeting.

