10.1.5 End-of-study visit

The following assessments will then be carried out at the EOS visit (28 days after the last dose of study drug) for every patient enrolled into the study.

- Performance status assessment.
- Physical examination.

- Vital signs.
- Serial 12-lead ECGs, in triplicate
- MUGA/ECHO.
- Serum pregnancy test.
- Clinical chemistry, hematology, coagulation and urinalysis.
- Blood sampling for PK
 - PK sampling in Arm B will be for BGB324 only - see Table 6.
- Disease assessment (if not performed within previous 28 days).
- Drug accountability.
- AEs assessment.
- Concomitant medications assessment.

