11.7 Patient Replacement

Patients in Arm A who discontinue during the DLT assessment period (Cycle 1 [21 days]) for any reason other than a DLT will be replaced. All other patients who discontinue study treatment will not be replaced.

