3.2.1 Objective Response Rate (ORR)

Patients included in the study must be assessed for response to treatment, Overall Response (OR) determined by Investigator based on appropriate radiographic imaging and consistent with RECIST 1.1.

Each patient will be assigned to one of the following ordered categories for OR (from best to worst responses): Complete response (CR), Partial response (PR), Stable disease (SD), Progressive disease, Not Evaluable (NE) or Not Applicable at each timepoint.

The Best Overall Response (BOR) is determined once all the data for the patient is known and is defined as the best overall response recorded from the initiation of treatment until disease progression or date of subsequent therapy across all tumour assessment.

ORR defined as percentage of patients with a BOR assessed as CR or PR, i.e. patients with response, divided by the number of patients in efficacy population.

The one-sided, within-group tests of proportion of responders, against the null hypothesis of a response rate $\leq 5\%$ (this being the observed response rate under current treatment). Values of $p < 0.2$ will be taken as sufficient evidence of a trend to justify further study.

For analysis of the ORR, summary tables will be generated, presenting the number and percentage of responders (i.e. patients with CR or PR) and non-responders in efficacy population.

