3.2.2 Best Percentage change in target lesion

Percentage change in target lesion size from baseline across all tumour assessment, where target lesion size is measured by the sum of the product of diameters of all target lesion sizes by the Investigator.

The Best percentage change is largest percentage change across all tumour assessment.

Patients who die due to progression of their disease prior to the first planned protocol assessment of response will be considered as having BOR of PD.

The first response assessed during the follow-up period will be used to confirm any previous CR or PR observed during the treatment period, provided that no new anti-tumoral treatment has been initiated during the follow-up period.

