5.1 Planned Analyses

Disposition analyses will be carried out using the Enrolled Population. Demographic and baseline characteristics analyses will be carried out using the Safety Population. Safety analyses will be carried out using the Safety Analysis Population. Efficacy analyses will be carried out using the Efficacy Population.

Summary statistics will be presented for continuous variables, by way of n, mean, standard deviation (SD), median, minimum (Min) and maximum (Max) and by way of group frequencies and percentages for categories of categorical variables. No statistical comparison of dose levels will be performed. Percentages will be calculated using the total subjects per dose cohort in the given population unless otherwise noted.

All data from this study will be presented in data listings. Unless otherwise noted, listings will be sorted by cohort dose level and subject.

Baseline is the most recent assessment prior to the first dose of a study drug (BGB324 or erlotinib) administration, i.e within 28 days before the first dose of study drug and after patient eligibility has been confirmed. Typically, this will be Cycle 1 Day 1 or screening. Where calculated, absolute change from baseline will be presented using the following formula for each parameter: Value at the visit/timepoint – value at baseline.

Data will be presented by dose/cohort and overall.

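### The Efficacy Population drops patients who were never scanned or had under one cycle from the Arm B response-rate denominator, which inflates the ORR and defeats the SAP's own early-death rules

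*SAP*

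**What the plan says.** SAP 4.5.3 sets two conditions for efficacy analysis: "The Efficacy Population will include all patients who receive ≥ 1 cycle of BGB324 and undergo an assessment of response post-baseline". Protocol 14.3.1 sets the same two. Both sections also allow patients with eligibility failures or major deviations to be excluded, case by case, at the meeting before database lock.

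SAP 3.2.1 defines the ORR as patients with a best overall response (BOR) of CR or PR, "divided by the number of patients in efficacy population". SAP 5.1 extends the set to everything else: "Efficacy analyses will be carried out using the Efficacy Population". The planned BOR, time-to-progression (TTP) and waterfall outputs in SAP 6.1.2 and 6.3 all carry it in their titles.

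Three other rules deal with patients who fail early:

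- SAP 3.2.2, on early deaths: any patients that "die due to progression of their disease prior to the first planned protocol assessment of response will be considered as having BOR of PD".
- SAP 3.2.3: "If a subject died without any radiological assessment, the progressive disease date is date of death".
- SAP Table 1, under 3.2.3: a patient in the row "No baseline evaluable or post-baseline radiological assessment" is censored at first treatment.

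The first scheduled on-treatment scan is at the end of Cycle 2 (6 weeks). Protocol 10.1.5 and 10.1.6 add a scan at the end-of-study visit, unless one was done in the previous 28 days, and at progression. Protocol 11.7 replaces only Arm A patients who leave during Cycle 1 for a reason other than a DLT; beyond that, "All other patients who discontinue study treatment will not be replaced".

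**The concern.** Entry to the denominator depends on what happens after treatment starts: the patient must stay on drug for a cycle and be available for a scan. Patients who fail this are mostly early deaths, losses to follow-up and consent withdrawals. A never-scanned patient cannot be a responder. A patient with less than one cycle is excluded even if scanned at the end-of-study visit, and is very unlikely to be a responder. Removing non-responders from the denominator can only raise the ORR and lower the p-value.

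The definition also works against the SAP's own intent. Sections 3.2.2 and 3.2.3 count early deaths as failures, but a patient with no post-baseline assessment is removed before either rule can apply. For TTP there is a further gap: the death rule and the Table 1 row give different answers for a patient who died unscanned, and no precedence is stated.

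The Arm B ORR is secondary and exploratory, but it carries the study's only formal test, and p<0.2 is the stated ground for further study. The estimate and interval will be read alongside it. In Arm C, leaving out deaths without a scan lengthens the estimated TTP.

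**Working it through.** **Inputs.** Arm B planned total 25 (9 + 16), null response rate 0.05, alternative 0.20 (Protocol 14.6, SAP 4.9); one-sided binomial test at 0.2 (SAP 5.7.3.1); Arm C maximum 14. The number excluded, k, is not in the documents and is varied.

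**The plan's own figures.** Protocol 14.6 and SAP 4.9 state a type I error of at most 0.73 and power of at least 0.0367 for rejecting at 4 or more responses in 25. These do not reproduce as labelled. P(X≥4 | n=25, 0.05) = 0.0341 and P(X≥4 | n=25, 0.20) = 0.766 without a futility stop. If no patient has stable disease, so that only a response prevents the stop, they are 0.0297 and 0.712. That is a separate problem, and nothing below depends on it.

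**Inflation of the estimate.** With R responders and k excluded non-responders, [R/(25-k)] ÷ [R/25] = 25/(25-k). This gives 1.14 at k=3, 1.25 at k=5, 1.47 at k=8 and 1.56 at k=9. If Arm B stops after stage 1, the factor is 9/(9-k).

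**Three responders, exact binomial against 0.05:**

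| Denominator | ORR | Exact 95% CI | One-sided p |
|---|---|---|---|
| 25 | 12.0% | 2.5 to 31.2% | 0.127 |
| 20 | 15.0% | 3.2 to 37.9% | 0.076 |
| 17 | 17.6% | 3.8 to 43.4% | 0.050 |

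**Pass/fail.** The smallest count with p<0.2 is 3 for every n from 17 to 25, and 2 for n from 12 to 16. At the boundary, 2 of 17 gives p=0.208 and 2 of 16 gives p=0.189; 2 of 25 would give 0.358. So the decision can change only from k=9.

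**Expected ORR and type I error.** Let a fraction e of all treated patients be dropped, all of them non-responders. The response rate among those retained is p/(1-e). Type I error is enumerated exactly with responders distributed Bin(25, 0.05), each non-responder dropped with probability e/0.95, and no futility stop.

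| e (assumed) | ORR at true 5% | ORR at true 20% | Type I error of p<0.2 test |
|---|---|---|---|
| 0 | 5.0% | 20.0% | 0.127 |
| 10% | 5.6% | 22.2% | 0.127 |
| 20% | 6.3% | 25.0% | 0.136 |
| 30% | 7.1% | 28.6% | 0.192 |
| 40% | 8.3% | 33.3% | 0.286 |

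Type I error reaches the nominal 0.2 at e = 30.9%.

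**Arm C.** Assume k scanless deaths among 14, all before any other event or censoring. Then the all-treated progression-free proportion is (14-k)/14 times the retained one. When the retained set reads 50%, the all-treated figure is 46.4%, 42.9% and 39.3% for k = 1, 2 and 3.

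**The case against.** The strongest reply is that little turns on this. Both documents call efficacy essentially exploratory. Further study is tied to p<0.2, and that result does not move until 9 of 25 (36%) are dropped. The rule of 4 or more responses is a count and is not touched. Entry requires ECOG 0 or 1, and scans at progression and end of study keep many early stoppers assessable, so 30 to 40% excluded may be unrealistic. With 1 to 3 dropped, 3 responders read 12.5 to 13.6% instead of 12.0%, well inside the interval. All of this stands, and it limits the weight of the point. It does not justify a denominator that can only err upwards.

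A second reply is that the definition can be read more generously. A missed scan might count as a not-evaluable assessment, since the Table 1 footnote treats a time point without imaging that way, and a cycle started might count as a cycle received, since SAP 5.6 counts cycles started. Neither is the natural reading: a patient who died unscanned has not undergone an assessment of response. It is true that the cycle condition is not defined. If the generous reading is intended, the text needs to say so.

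Third, exclusions are documented, Listing 16.2.3 names the excluded patients, and tumour data are listed on the Safety Population. A reader could rebuild the all-treated rate, but no planned table reports it.

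For Arm C, TTP is descriptive, and patients enter after at least 12 weeks of erlotinib without progression, so scanless deaths may be few. Also, the death rule in SAP 3.2.3 covers death from any cause, whereas 3.2.2 is limited to progression deaths. That difference should be settled when the text is revised.

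**Conclusion.** The concern holds. On its plain reading, SAP 4.5.3 removes never-scanned patients and those with under one cycle from the ORR denominator, and the early-death rules in SAP 3.2.2 and 3.2.3 have no effect for patients without a post-baseline assessment. The inflation factor 25/(25-k) is exact for never-scanned patients. For patients with under one cycle it assumes that none responded.

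The damage is to the estimate, its interval and the p-value. The test decision is unaffected up to 8 dropped, and type I error stays below 0.2 until about 31% are dropped. These results rest on an assumed range of exclusions and on a full Arm B of 25.

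The discretionary exclusions for eligibility or deviations add a separate risk. They are decided before lock, when open-label, investigator-assessed responses can already be known. The direction of that bias is not fixed. The plan should be changed, but the point does not undermine the trial.

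**What to change.** - **Arm B:** make the ORR and its binomial test primary on all Arm B patients who received at least one dose of BGB324, and count patients without a post-baseline assessment as non-responders. Report the present Efficacy Population, with any deviation exclusions, as a sensitivity analysis, and define what counts as one cycle.
- **Arm C:** run TTP on all treated patients. State that the SAP 3.2.3 death rule takes precedence over the Table 1 row for patients with no post-baseline scan, and whether it is meant for death from any cause, as now worded. Other unscanned patients stay censored at first dose, so this restores only deaths without a scan.
- **Consistency:** amend Protocol 14.3.1 and SAP 3.2.1, 4.5.3, 5.1 and 6.1.2 together.

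The cost is wording in two documents and one extra table, from data already listed on the Safety Population. No visit, treatment or sample size changes. The reported ORR will be somewhat lower if any patients go unscanned or receive less than one cycle.
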